5. STUDY DESIGN

a. STUDY TYPE & DESIGN & SCHEDULE

ii. STUDY DESIGN:

This is a prospective observational single-centre cohort study of 210 patients who are LT recipients followed up for 12-months, to determine the utility of the QFM-dscfDNA in monitoring and managing immunosuppression post LT.

Consenting adults (aged 18 years and over) undergoing LT at Austin Health will be invited for enrolment in the study in the pre-transplant clinic, during outpatient assessment or on admission to hospital prior to LT. Written informed consent will be obtained prior to enrolment. Recipients under 18 years of age, those who do not consent their participation and those who are undergoing multi-organ transplantation will be excluded from the study.

The design of this study will enable the researchers to examine if the QFM-dscfDNA tests can be used in LT recipients to accurately diagnose and predict acute rejection and infective complications, monitor treatment responses, and improve healthcare resource utilisation.

iii. INTERVENTION:

Participants will receive the standard of care after LT, with serial additional blood sampling required for QFM-dscfDNA testing:

Standard of care after LT: Clinical care of LT recipients is directed by a team of experienced clinicians. Potential recipients are selected based on clinical urgency and donor–recipient matching. LT is performed as per protocol. Routine immunosuppression comprising steroids, a calcineurin inhibitor and an antimetabolite will be prescribed. Routine protocol liver biopsies are not performed to monitor organ health. Routine blood tests (FBE, UEC, LFTs and serum drug levels) are performed regularly to monitor the clinical course. Recipients are closely followed up as outpatients after discharge. Complications after LT may result in the deterioration of clinical status and abnormalities on routine blood tests. Imaging,

endoscopy and/or liver biopsies are performed for diagnosis and managed accordingly.

• Additional blood sampling: The intervention requires serial additional blood sampling of recipients, which will be performed when routine blood sampling for standard of care is undertaken wherever possible, to reduce the need for additional venesection.

As per **Figure 1**, 15-30ml will be collected to perform the QFM-dscfDNA testing and to be stored for future research purposes as per the extended consent obtained. Blood sampling will occur in the inpatient and outpatient setting at Austin Health, to ensure that investigators have direct and timely access to the blood samples. Blood samples will be processed in the Olivia Newtown John Cancer Research Institute (ONJCRI) and stored in a specially allocated -80°C freezer in the Liver Transplant Unit (LTU), both located at the same campus.

As per **Table 1**, blood will be collected pre-transplant (baseline) and post-transplant on days 1, 3 and 5; week 1 and 2; and months 1, 2, 4, 6 and 12 from enrolled participants (11 time points x 210 recipients = 2310 tests). We estimate that approximately 150 clinical events of acute rejection and infective complications will occur throughout the course of this study. As a standard of care, these clinical events require close surveillance with routine blood tests. In conjunction with the routine blood tests, additional blood will be sampled to capture the dynamics of QFMdscfDNA during these clinical events (3 time points taken 1-3 days apart, 3 x 150 events = 450 tests). A total of 2760 QFM-dscfDNA measurements will be performed in this study (2310 + 450 tests).

Table 1: Schedule of serial additional blood sampling			
Time		Additional blood sampling	
Before LT		x 1	
Post LT			
Day	1	x 1	
	3	x 1	
5		x 1	
Week	1	x 1	
	2	x 1	

Month	1	x 1
	2	x 1
	4	x 1
	6	x 1
	12	x 1
If a clinical event occurs		x 3 (taken 1-3 days apart)

The donor blood samples required for dscfDNA processing will be obtained during organ procurement, in accordance with the Human Research Ethics Committee for Donate Life and the Australian Red Cross Blood Services (application in progress).

iv. DATA COLLECTION, USE AND DISSEMINATION:

The following data (as defined in '**4.c OUTCOME MEASURES**' and '**5.a.iii INTERVENTION**') will be prospectively collected:

- Standard of care clinical variables
- Standard of care blood tests
- Clinical events
- Blood sampling
- Health expenditure

All data will be collected in identifiable form correlated to the patient's Austin Health UR, but will be re-identified or coded for use.

Results from this study will be published and presented at conferences in de-indentified or cohort form. Furthermore, [name] and [name] will use the results from this study towards their PhDs in Medicine, Dentistry and Health Sciences at the University of Melbourne.

v. TIMELINE:

The aims of this study can be accomplished within a four-year period. Austin Health performs approximately 75 adult LTs per year, therefore recruitment of 210 participants is achievable within three years. The QFM-dscfDNA levels laboratory analyses will commence after each recipient has completed a 12-month follow-up, thus the completion of this will correlates with year four, when post trial analyses and preparation of results for publication will occur.

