LFTs are extremely sensitive tests for organ injury but have poor specificity for LT complications⁷. As a screening tool, they can lead to a series of radiological and endoscopic investigations that often culminate in an invasive liver biopsy to confirm the clinical event⁸. Acute rejection is treated with increased doses of immunosuppressants while infection necessitates dosage reduction. This relatively 'reactive' approach precludes preventive intervention by predictive adjustments.

Researchers at Austin Health have shown that the use of an immune monitoring blood test, QuantiFERON-Monitor (QFM), identifies recipients at risk of early rejection or infective complications. Austin Health researchers have also developed a novel blood test to rapidly measure organ injury using donor-specific cell-free DNA (dscfDNA).

We propose a prospective observational cohort study of 210 patients who are LT recipients followed up for 12-months to determine the utility of combining the two blood tests (QFM-dscfDNA) in monitoring and managing immunosuppression post LT. Our primary hypothesis is that the QFM-dscfDNA tests can be used to accurately diagnose the occurrence of rejection or infective complications after liver transplantation. The secondary hypotheses are that QFM-dscfDNA tests can be used to predict acute rejection or infective complications, monitor treatment responses and improve healthcare resource utilisation.

There is a clear and urgent need for accurate clinical tools to personalise immunosuppression. Confirmation of our hypotheses facilitates a "predictive" rather than the current "reactive" approach to immunosuppression. Our approach can potentially minimise the need for complex diagnostic tests including ultrasound, computed tomography, magnetic resonance imaging, endoscopy and liver biopsies - with significant clinical and economic benefits.

If positive, the findings of this study will lead to a prospective randomised multi-centre trial comparing the standard and precision approaches in LT. If validated in LT, we foresee that the predictive approach to immunosuppression is readily translatable for evaluation in other solid organ transplantations. With over 125,000 solid organ transplantations being performed

worldwide annually, the clinical and economic implications of this study could be substantial.

c. BACKGROUND INFORMATION

i. SCIENTIFIC BACKGROUND

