4. STUDY OBJECTIVES

a. HYPOTHESIS

The primary hypothesis is that the QFM-dscfDNA tests can be used to accurately diagnose the occurrence of acute rejection and infective complications after LT.

The secondary hypotheses are that the QFM-dscfDNA tests can be used to:

- Predict acute rejection and infective complications.
- Monitor treatment responses.
- Improve healthcare resource utilisation.

b. STUDY AIMS

- To examine if the QFM-dscfDNA tests can be used to accurately diagnose acute rejection and infective complications after LT.
- To examine if the QFM-dscfDNA tests can be used to predict acute rejection or infective complications, monitor treatment responses, and improve healthcare resource utilisation.

c. OUTCOME MEASURES

i. DEFINITION OF CLINICAL EVENTS:

- Rejection: The gold standard for diagnosing acute rejection is based on histopathologic grading on liver biopsy. It is often difficult to differentiate mild rejection from ischemia-related cholestasis early after LT and clinical evaluation may lead to observation rather than active treatment if temporal improvement is demonstrated. We thus employed the strict definition requiring consistent histology and treatment of rejection (tBPAR), an acceptable standard for clinical trials^{18,19}.
- Infective complications: Infection endpoints will be defined according to the criteria of 'no', 'probable' or 'definite' infection derived from the international sepsis forum consensus conference on '*Definitions of Infection in the Intensive Care Unit*^{'20}.

i. VARIABLES TO BE MEASURED:

- Standard of care clinical variables: Donor and recipient factors such as donor risk index, model for end-stage liver disease score, waiting list time, primary indication for transplantation, operative factors and immunosuppression regimens can influence post LT outcomes. These characteristics will be prospectively recorded for analysis.
- Standard of care blood tests: Routine blood tests including full blood count (FBE), urea and electrolytes (UEC), LFTs and serum drug levels are used for clinical decision making as a standard of care. The results of each test will be prospectively recorded.

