8. STATISTICAL METHODS

a. SAMPLE SIZE ESTIMATION & JUSTIFICATION

We propose enrolling a total of 210 LT recipients during a three-year recruitment period. This timeframe is anticipated to be easily feasible as the LTU performs an average of 75 adult LTs each year. Most recipients will fulfil the trial's inclusion and exclusion criteria; hence non-eligibility (including refusal of informed consent) is anticipated to be low (about 5%). In addition, lost-to-follow-up (including death) is anticipated to be very low (about 1-2%) during the 12-month follow-up².

In preliminary research from Austin Health¹⁶, 31% of the recipients experienced tBPAR as the first event after LT while 41% experienced a 'probable'/'definite' infective complication as the first event after LT, both within a 12-month follow-up period. To be conservative, we assume 30% of our recruited recipients will experience at least one tBPAR and 40% at least one infective complication. The sample size of 210 LT recipients will allow us to estimate a fair AUC of 0.7 using a two-sided 95% confidence interval with precision \pm 0.081 for tBPAR and \pm 0.075 for infection and a good AUC of 0.8 with a precision of \pm 0.075 for tBPAR and \pm 0.069 for infection^{21,22}.

b. POWER CALCULATIONS

This sample size will provide a power of 99.7% to show that the combination has any ability to discriminate between those with and without tBPAR and 99.9% power between those with and without infection, (null hypothesis AUC of 0.5), assuming that we observe a fair AUC of 0.7 with 5% alpha²¹.

c. STATISTICAL METHODS TO BE UNDERTAKEN

All participants will be included in the final analyses. Diagnostic performance of QFM and dscfDNA combined for the first tBPAR and the first 'probable'/'definite' infective complication will be assessed by evaluation of sensitivity, specificity, the positive and negative predictive value and diagnostic accuracy. Diagnostic accuracy will be evaluated by determining the AUC and two-sided 95% confidence interval. Given that QFM and dscfDNA outcomes are measured repeatedly over 12 months, we will initially summarise these outcomes across time-points using the average, nadir, standard deviation and slope and fit a logistic regression model.

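### For the tBPAR co-primary endpoint, LFTs are both the comparator and a trigger for the biopsy that defines a case, so the all-participant AUC comparison leans towards LFTs by an unknown amount

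*Protocol*

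**What the plan says.** - **Comparison.** Protocol section 4.c (Primary endpoints) sets the accuracy of QFM and dscfDNA, alone and combined, against LFTs. The measure is the AUC, for the first tBPAR and for the first infective complication.
- **Reference standard.** Section 4.c (Definition of clinical events) counts a tBPAR only when histology fits rejection and the rejection is treated. On mild rejection that is hard to tell from cholestasis early after transplant, it says that "clinical evaluation may lead to observation rather than active treatment if temporal improvement is demonstrated".
- **Who is biopsied.** Section 5.a.iii states: "Routine protocol liver biopsies are not performed to monitor organ health". Biopsy is one of the investigations that follow clinical deterioration or abnormal routine blood tests, and those tests include LFTs. Section 3.b says of LFTs as a screening tool that "they can lead to a series of radiological and endoscopic investigations that often culminate in an invasive liver biopsy to confirm the clinical event".
- **Masking.** Under section 4.c, QFM and dscfDNA are assayed in batches after the 12-month follow-up so that they cannot affect care. LFTs are in open clinical use.
- **Analysis set.** Section 8.c: "All participants will be included in the final analyses".

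**The concern.** The comparator helps to decide who receives the reference standard; the new tests cannot. A rejection that occurs with unremarkable LFTs is less likely to be biopsied, and without a biopsy it cannot be labelled tBPAR. In an all-participant analysis it then counts as a correct negative for LFTs and, if dscfDNA or QFM flags it, as a false positive for the new test. This is partial-verification bias with a known direction.

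At stake is how the tBPAR comparison can be read. If the new tests beat LFTs despite the bias, the result is conservative. If they do not, nobody can tell whether the tests are no better or whether the labelling hid the difference. The point does not extend to the infection endpoint, whose definition does not depend on liver biopsy.

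**Working it through.** **1. The protocol's own figures.** Inputs from sections 8.a and 8.b: "We propose enrolling a total of 210 LT recipients during a three-year recruitment period"; "we assume 30% of our recruited recipients will experience at least one tBPAR and 40% at least one infective complication"; "assuming that we observe a fair AUC of 0.7 with 5% alpha"; "null hypothesis AUC of 0.5". This gives 0.30 × 210 = 63 tBPAR cases against 147 non-cases, and 0.40 × 210 = 84 infections against 126.

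Obuchowski binormal variance: V = 0.0099·exp(−a²/2)·[(5a² + 8) + (a² + 8)/k], with a = 1.414·z(AUC) and k = non-cases/cases. SE = √(V/cases).

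- tBPAR, AUC 0.7: a = 0.7415 and k = 147/63 = 2.333. V = 0.0099 × 0.7596 × (10.749 + 3.664) = 0.1084, so SE = √(0.1084/63) = 0.0415. Half-width = 1.96 × 0.0415 = 0.0813 (stated 0.081).
- The other half-widths are 0.0752 (infection, 0.7), 0.0754 (tBPAR, 0.8) and 0.0690 (infection, 0.8). The stated values are 0.075, 0.075 and 0.069.
- Power for tBPAR: under the null a = 0, V = 0.0099 × (8 + 8/2.333) = 0.1131 and SE₀ = 0.0424. (0.2 − 1.96 × 0.0424)/0.0415 = 2.82, so power is 99.76% (stated 99.7%). For infection it is 99.93% (stated 99.9%).

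All of these reproduce and none is disputed. They concern a single AUC, not the difference from LFTs.

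**2. Effect of LFT-driven biopsy, threshold model.** The protocol gives no biopsy rate, share of rejections missed or LFT AUC, so everything in this step is assumed. LFT and new-test values are normal with unit SD. Rejection shifts them by √2·z(0.70) and √2·z(0.80). Within-class correlation is 0.3. A participant is biopsied if LFT plus noise (0.5 SD unless stated) exceeds a cut. The label is positive only if rejection is present and biopsied. Each setting has 400,000 simulated participants. Labelled tBPAR = true rejection × share biopsied, for example 0.40 × 0.75 = 30% and 0.40 × 0.55 = 22%.

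| True rejection | Rejections biopsied | LFT AUC | New-test AUC | Order |
|---|---|---|---|---|
| 35% | 96% | 0.73 | 0.80 | kept |
| 35% | 91% | 0.76 | 0.80 | kept |
| 35% | 84% | 0.79 | 0.80 | kept, barely |
| 40% | 75% down to 55% | 0.83 up to 0.89 | 0.80 to 0.79 | reversed |
| 40%, 60% of participants biopsied, noise 2 SD | weaker LFT trigger | 0.75 | 0.77 | kept |

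**3. Second selection model.** Biopsy probability is logistic in LFTs (slope 1 to 2 per SD), correlation is 0 to 0.5, and labelled prevalence is held at the protocol's 30%. There are six settings per row.

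| Rejections biopsied | LFT AUC | New-test AUC | Reversed |
|---|---|---|---|
| 95% | 0.71-0.73 | 0.79-0.81 | none |
| 90% | 0.73-0.75 | 0.79-0.81 | none |
| 80% | 0.75-0.79 | 0.77-0.81 | 1 of 6 |
| 70% | 0.76-0.82 | 0.75-0.81 | 4 of 6 |
| 60% | 0.77-0.84 | 0.71-0.80 | 6 of 6 |

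If the true AUCs are 0.75 and 0.80, reversal starts at 90% biopsied (0.793 v 0.786, steep selection, correlation 0).

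**4. Controls.** With biopsy unrelated to LFTs (half biopsied, 40% rejection), the AUCs fall to 0.65 and 0.73 and the order is kept. LFT-driven selection is therefore what favours LFTs. With a strong separate clinical trigger (half biopsied), LFTs reach only 0.72-0.75 against 0.80.

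**5. Remedies.** Restricting to biopsied participants gives LFTs 0.64-0.65 and the new test 0.78 in the reversed settings of step 2, so LFTs are then understated. Inverse-probability-of-biopsy weighting returns about 0.70 and 0.80 when biopsy depends on LFTs alone. At N = 210 under strong LFT selection, the weighted AUC difference has an SD of 0.12 against 0.04 for the unweighted one, a ratio of 0.12/0.04 = 3.

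**The case against.** - **The target is tBPAR, not latent rejection.** On the protocol's chosen definition, a participant never biopsied or treated is a true negative. This stands as far as the label goes, and is why the all-participant AUC should be kept. It does not remove the problem: LFTs helped to produce the label and the new tests could not.
- **LFTs are described as extremely sensitive.** Section 3.b says so for organ injury. If that carries over to rejection, few rejections go unbiopsied and the upper rows of the tables apply. Section 5.a.iii also names clinical deterioration as a trigger. Both points stand and limit the size.
- **Corrections belong in the SAP.** The absence of a correction is not the point. The comparator, the reference standard, for-cause biopsy and the all-participant set are all fixed in the protocol, and together they create the bias.

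A reader might go further than the documents allow in three ways:

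- *That the order of the tests will be reversed.* Reversal needs a substantial share of rejections unbiopsied under strong LFT selection, or a small true difference. The protocol gives no figure that establishes either.
- *That LFTs decide whether rejection is treated.* Section 4.c refers only to clinical evaluation and improvement over time, without naming LFTs. Section 3.b links LFT changes to immunosuppression dosing in general. Influence on the decision to treat is an inference.
- *That the all-participant and biopsied-only AUCs bracket the truth.* They err in opposite directions for LFTs in these simulations, but nothing guarantees that they are bounds.

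Scoring unbiopsied participants as negative is likewise implied by the definition and the analysis set, not stated.

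**Conclusion.** The point holds for the tBPAR co-primary endpoint. Followed as written, the comparison with LFTs favours LFTs; the amount cannot be fixed from the protocol. Under assumed true AUCs of 0.70 and 0.80, LFTs rise to about 0.73-0.79 when 84-96% of rejections are biopsied. The gap shrinks from 0.10 to between 0.07 (0.80 − 0.73) and 0.01 (0.80 − 0.79), with no reversal in those settings. With 55-75% biopsied and strong LFT selection, LFTs reach 0.83-0.89 and the order reverses. In every setting where LFTs alone drove biopsy, the LFT AUC was inflated. Even a shift of a few hundredths matters beside the protocol's half-width of 0.075-0.081 for a single tBPAR AUC. The bias runs against the sponsor's hypothesis, so a positive finding is safe and a null or negative one is not interpretable.

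**What to change.** Keep the all-participant AUC for tBPAR as defined, and state that its comparison with LFTs is biased towards LFTs. Report beside it, as sensitivity analyses and not as bounds:

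1. the AUC comparison among biopsied episodes;
2. a verification-bias-corrected AUC (inverse-probability-of-biopsy weighting or Begg-Greenes), with biopsy modelled on the recorded LFTs and clinical variables, where biopsies at low LFTs are frequent enough to support it;
3. an analysis with histology alone as the reference, whether or not the rejection was treated.

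If the correction is not supported, limit the conclusion against LFTs to biopsied or suspected episodes. Confirm that every biopsy result is recorded, including those that did not lead to treatment.

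The cost is extra analysis, largely on data already being recorded, and a less precise corrected estimate: its SD can be up to about three times the uncorrected one under strong LFT selection at N = 210. The correction also assumes that biopsy depends only on recorded variables. No protocol biopsies are needed.

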6. STUDY POPULATION

a. RECRUITMENT PROCEDURE

All patients who are being assessed for or awaiting a LT will be screened, approached, provided with recruitment documentation and consented prior to undergoing LT.

Austin Health performs approximately 75 adult LTs per year for the treatment of end-stage liver disease, fulminant liver failure and hepatocellular carcinoma. All patients referred for consideration of LT are managed by the LTU. They are therefore seen in one outpatient clinic, undergo assessment in one outpatient setting and treated by one inpatient team. This will assist in identification of appropriate patients.

Treating clinicians will be made aware of this cohort study and the identification of participants will require referral from the treating clinician. Patients will be recruited from outpatient clinics, during outpatient assessment and on the inpatient ward prior to LT.

Research coordinators will approach patients in person, provide them with recruitment documentation, and be available to explain the nature of the research. Individual written informed consent will be obtained prior to the patient undergoing LT.

b. INCLUSION CRITERIA

The inclusion criteria are:

- Patients aged 18 years or above.
- Undergoing LT.
- Able to provide written informed consent.

c. EXCLUSION CRITERIA

The exclusion criteria are:

- Patients aged under 18 years.
- Unable to provide written informed consent at any stage.
- Undergoing multi-organ transplantation

Patients undergoing multi-organ transplantation will be excluded as dscfDNA will not specifically reflect donor liver injury in this setting.

d. Consent

Individual consent will be obtained from all participants without a waiver of consent.

In the event that a patient is too unwell and unable to consent, but is expected to recover and be able to provide consent (which may happen for example in fulminant hepatic failure), consent for initial enrolment will be obtained from the next of kin or person responsible/medical treatment decision maker. Following recovery from LT, patient consent for ongoing follow up and for use of data collected at enrolment will be obtained.

Consent will be extended in scope. This means that participants are consenting to the use of their blood samples or data in future research projects that are extensions of or closely related to this study, or in the same general area of research.

